9.13 Other Ethical and Regulatory Issues

If a significant safety issue is identified, either from an individual case report or review of aggregate data, then the Sponsor will issue prompt notification to all parties – Regulatory Authorities, Investigators, and IECs/IRB.

A significant safety issue is one that has a significant impact on the course of the clinical study or program (including the potential for suspension of the development program or amendments to protocols) or warrants immediate update of informed consent.

9.14 Liability and Insurance

The Sponsor will take out reasonable third-party liability insurance coverage in accordance with all local legal requirements. The civil liability of the Investigator, the persons instructed by him or her and the hospital, practice, or institute in which they are employed and the liability of the Sponsor with respect to financial loss due to personal injury and other damage that may arise as a result of the carrying out of this study are governed by the applicable law.

The Sponsor will arrange for patients participating in this study to be insured against financial loss due to personal injury caused by the study drug being tested or by medical steps taken in the course of the study.

9.15 Publication Policy

By signing the study protocol, the Investigator agrees with to the use of results of the study for the purpose of national and international registration, publication and information for medical and pharmaceutical professionals. If necessary, Regulatory Authorities will be notified of the Investigator's name, address, qualifications and extent of involvement.

An Investigator shall not publish any data (poster, abstract, paper, etc.) without having consulted with the Sponsor in advance. Details are provided in a separate document.

11 APPENDICES

11.1 Appendix 1: WHO Classification of Acute Myeloid Leukemia

Acute myeloid leukemia (AML) and related neoplasms
AML with recurrent genetic abnormalities
AML with t(8;21)(q22;q22.1);RUNX1-RUNX1T1
AML with inv(16)(p13.1q22) or t(16;16)(p13.1;q22);CBFB-MYH11
AML with t(9;11)(p21.3;q23.3);MLLT3-KMT2A
AML with t(6;9)(p23;q34.1);DEK-NUP214
AML with inv(3)(q21.3q26.2) or t(3;3)(q21.3;q26.2); GATA2, MECOM
AML (megakaryoblastic) with t(1;22)(p13.3;q13.3);RBM15-MKL1
Provisional entity: AML with BCR-ABL1
AML with mutated NPM1
AML with biallelic mutations of CEBPA
Provisional entity: AML with mutated RUNX1
AML with myelodysplasia-related changes
Therapy-related myeloid neoplasms
AML, NOS
AML with minimal differentiation
AML without maturation
AML with maturation
Acute myelomonocytic leukemia
Acute monoblastic/monocytic leukemia
Pure erythroid leukemia
Acute megakaryoblastic leukemia
Acute basophilic leukemia
Acute panmyelosis with myelofibrosis
Myeloid proliferations related to Down syndrome
Transient abnormal myelopoiesis (TAM)
Myeloid leukemia associated with Down syndrome

11.2 Appendix 2: ECOG Performance Status

Grade	Description
0	Normal activity. Fully active, able to carry on all pre-disease performance without restriction
1	Symptoms, but ambulatory. Restricted in physically strenuous activity, but ambulatory and able to carry out work of a light or sedentary nature (e.g. light housework, office work)
2	In bed < 50% of the time. Ambulatory and capable of all self-care, but unable to carry out any work activities. Up and about more than 50% of waking hours
3	In bed > 50% of the time. Capable of only limited self-care, confined to bed or chair more than 50% of waking hours.
4	100% bedridden. Completely disabled. Cannot carry on any self-care. Totally confined to bed or chair
5	Dead

11.3 Appendix 3: Child-Pugh Score

Measure	1 point	2 points	3 points
Total bilirubin, mg/dL	<2	2–3	>3
Serum albumin, g/dL	>3.5	2.8–3.5	<2.8
Prothrombin time, INR	<1.7	1.7–2.3	>2.3
Ascites	Absent	Slight	Moderate
Hepatic encephalopathy	None	Grade I–II	Grade III–IV
Child-Turcotte-Pugh (CTP) Class obtained by adding score for each parameter (total points) Class A: 5-6 points Class B: 7-9 points Class C: 10-15 points			

Kasper, Dennis L., et al. Harrison's Principles of Internal Medicine. 19th edition. New York: McGraw Hill Education, 2015.

[figure not shown]
[figure not shown]

7.9	Demographics and Baseline Characteristics	27
7.10	Medical History and Prior and Concomitant Medications	28
7.11	Pharmacokinetic Data	28
7.11.1	Concentration Values	31
7.11.2	Calculation of the Actual Sampling Times	31
7.11.3	Pharmacokinetic Analysis	31
8.	REFERENCES	32
9.	LIST OF TABLES, FIGURES AND LISTINGS	33
9.1	Tables	33
9.2	Listings	34
9.3	Figures	36

LIST OF ABBREVIATIONS

AE	Adverse Event
AML	Acute Myeloid Leukemia
AUC _{tau}	Area Under the Plasma Concentration-Time Curve Over the Dosing Interval
AUC _{tau ss}	Area Under the Plasma Concentration-Time Curve Over the Dosing Interval at Steady State
BID	Twice a day
CBR	Clinical Benefit Rate
CI	confidence interval
CL/F	Apparent Total Clearance of the Drug from Plasma After Oral Administration
C _{max}	Maximum Observed Plasma Concentration
C _{max ss}	Maximum Observed Plasma Concentration at Steady State
CR	Complete Remission
CRF	Case Report Form
CRi	Complete Remission with Incomplete Hematologic Recovery
CSR	Clinical Study Report
C _{trough}	Trough plasma concentration
ECG	Electrocardiogram
EDC	Electronic Data Capture
EFR	Evaluable for Response
FAS	Full Analysis Set
GCP	Good Clinical Practice
IWG	International Working Group
LLN	Lower Limit of Normal
LLQ	Lower Limit of Quantification
MedDRA	Medical Dictionary for Regulatory Activities
MR	Metabolic Ratio
OCRR	Overall Complete Remission Rate
PID	Percentage of Intended Dose
PK	Pharmacokinetic
PR	Partial Remission
PT	Preferred Term
QD	Once Daily

Rac AUC	Accumulation Ratio for AUC
Rac C _{max}	Accumulation Ratio for C _{max}
RDI	Relative Dose Intensity
RFS	Relapse-Free Survival
SAE	Serious Adverse Event
SC	Steering Committee
SOC	System Organ Class
SOP	Standard Operating Procedure
std	Standard Deviation
t _{1/2}	Terminal Half-Life
t _{1/2 eff}	Effective Elimination Half-Life at Steady State
TEAE	Treatment Emergent Adverse Event
t _{max}	Time Corresponding to Occurrence of Maximum Observed Plasma Concentration
t _{max ss}	Time Corresponding to Occurrence of Maximum Observed Plasma Concentration at Steady State
ULN	Upper Limit of Normal
V _{ss} /F	Apparent Volume of Distribution at Steady State after Oral Administration
WHO	World Health Organization

1. STUDY OBJECTIVES

1.1 Primary Objectives

The primary objectives of the study are:

Part 1:

- To determine the optimum dose of ASLAN003 monotherapy based on the efficacy, safety and tolerability profile in Acute Myeloid Leukemia (AML) patients who are ineligible for standard therapy.

Part 2:

- To provide a preliminary estimate of the efficacy of ASLAN003 at the optimum dose selected from Part 1.

1.2 Secondary Objectives

Part 1

- To evaluate the pharmacokinetics (PKs) of ASLAN003 and its metabolite LAS186558 in patients with AML.

Part 2

- To further assess the safety and tolerability data of ASLAN003 at the optimum dose selected from Part 1.

1.3 Exploratory Objectives

Part 1:

- To examine the myeloid differentiation effects of ASLAN003 using assays including but not limited to an *ex vivo* flow cytometry assay.
- To explore possible relationships between molecular abnormalities and measures of clinical response in patients with AML.

2. Study Design

2.1 Overall Study Design

This study is designed as a multicenter, single arm, non-randomized phase IIA study to evaluate ASLAN003 as a monotherapy in patients with AML.

AML patients who are ineligible for standard treatment including, but not limited to the following conditions, will be enrolled in the study:

- Newly diagnosed patients who are ineligible for standard therapy i.e., standard dose induction chemotherapy and reduced dose chemotherapy
- Patients with relapse from prior remission
- Patients with failed response to prior therapy including chemotherapy, hypomethylating agents, and bone marrow transplantation.

[figure not shown]
Part 1:

Up to a total of 24 patients will be enrolled into Part 1 of this study – 6 patients in each dose cohort (ASLAN003 100 mg once daily (QD), 200 mg QD, 100 mg twice daily (BID) and 200 mg BID, respectively). Once 6 patients have been enrolled into the cohort of 100 mg QD, recruitment will be started in the cohort of 200 mg QD. The same rule applies to the 100 mg BID and 200 mg BID cohorts. A steering committee (SC) meeting will be set up and meet to review all safety data. Details of the SC outcome will be specified in the SC charter.

Part 2:

An expansion cohort of 20 patients will be recruited to study the optimum dose selected by the SC. The optimum dose will be selected from at least one cohort showing tolerable safety profile and clinical benefit in disease presentation. Details will be specified in the SC charter.

Figure 1: Study Design

2.2 Methods of Assigning Patients to Treatment Groups

At Screening, each patient will receive a unique Screening number from electronic data capture system (EDC). The number will start with "S" and be followed by 4 digits starting with S0001 for Part 1 and S2001 for Part 2.

Part 1:

Following confirmation of eligibility, all patients will be sequentially assigned to the dose levels after being screened for eligibility and providing consent. At administration of the first dose of study drug, patients will be assigned with a 4-digit patient number in the order in which they are enrolled in the study starting from 0001. Enrolled patients who drop out of the study before receiving the study drug will retain their Screening number.

Part 2:

Following confirmation of eligibility and providing consent, all patients will be sequentially assigned to the dose level selected from Part 1. At administration of the first dose of study drug, patients will be assigned with a 4-digit patient number in the order in which they are enrolled in the study starting from 2001. Enrolled patients who drop out of the study before receiving the study drug will retain their Screening number.

2.2.1 Procedures for Randomization

Not applicable.

3. ENDPOINTS

3.1 Efficacy Endpoints

Efficacy will be evaluated in accordance with the IWG Criteria¹⁶ for AML (Cheson, 2003). Definitions of the primary and secondary efficacy variables are described in Sections 3.1.1 to 3.1.6. In addition, the following principles will be applied:

For the evaluation of OCRR, TTR and TTCR, if bone marrow and peripheral blood assessments are both performed, the assessment date used will be the date of the bone marrow assessment. If only blood assessments are performed, the assessment date will be the date of the blood assessment.

For RFS, the date of relapse will be the assessment date of the first component that fulfills the criteria for relapse (Section 3.1.2). For example, if both the peripheral blood and bone marrow were indicative of relapse, but the blood assessment was performed first, then the date of relapse would be the date of the peripheral blood assessment. Similarly, if relapse was first detected due to the development of cytologically proven extramedullary disease, the date of detection for the extramedullary disease would be the date of relapse, even if the bone marrow and peripheral blood assessments were not performed until a later date.

3.1.1 Overall Complete Remission Rate

Overall complete remission rate (OCRR) is a co-primary endpoint in Part 1 and the primary endpoint in Part 2. It will be derived programmatically from the BM aspiration and peripheral blood results based on the IWG Criteria¹⁶ for AML (Cheson, 2003) as described below.

For patients without sufficient archival BM sample, BM aspiration will be performed during Screening. All patients will receive bone marrow aspiration for efficacy assessment on Day 1 of Cycle 2, 3, 4, 5 and will be repeated every 3 cycles after Cycle 5. Patients who've already achieved CR could omit the bone marrow aspiration at subsequent visits if there is a normal complete blood count with differential of the peripheral blood. Investigator may perform more frequent exam if required based on clinical judgment.

BM aspiration smears will be processed locally.

Following treatment discontinuation, patients who have achieved a CR or CRi, will continue to be followed up for every 12 weeks to assess the relapse free survival. For patients who have not achieved a CR or CRi during treatment, no further follow-up is required following treatment discontinuation.

These criteria categorize the visit response into the following response classifications:

- *CR with incomplete recovery of neutrophils and platelets (CRi):*

Achievement of CRi requires patients to satisfy all of the following:

- A disappearance of blasts in the peripheral blood.
- A decrease in BM blasts to <5% total BM nucleated cells demonstrated in BM aspirate.
- Absence of Auer rods
- No persistent extramedullary leukaemia

- *Complete Remission:*

Patient satisfies all of the criteria above and in addition has:

- Recovery of Neutrophils to $\geq 1.0 \times 10^9/L$ and Platelets to $\geq 100 \times 10^9/L$
- Transfusion-independence

- *Partial Remission:*

A PR is defined as recovery of neutrophils to $\geq 1.0 \times 10^9/L$ and Platelets to $\geq 100 \times 10^9/L$ and either:

- If the pre-treatment bone marrow blast percentage was 50% to 100%, the percentage of blast must decrease to a value between 5% and 25%
- If the pre-treatment BM blast percentage was 20% to less than 49%, they must decrease by at least half to a value of more than 5%

- A reduction in BM blast cells to <5% but with persistence of Auer rods.

- *Treatment failure:*

Failure to meet the criteria for CR, CRi or PR after 4 cycles of treatment will result in a best response of treatment failure.

For the evaluation of OCRR, a binary variable will be created to indicate complete response status of each patient (complete responder or non-responder) defined as follows:

A patient will be classified as a complete responder if either of the following are achieved during the study and prior to starting subsequent AML treatment:

- Achievement of CR
- Achievement of CRi

Patients who do not satisfy the OCRR criteria outlined above (including patients with PR, treatment failure and any patients without evaluable post-treatment assessments) will be classified as non-responders for the assessment of OCRR.

Best response status will also be assessed. A patient's best response is defined as the best AML visit response observed, ranked in the following order:

CR > CRi > PR > Treatment failure.

OCRR is defined as the number (%) of patients with a best response of complete remission (CR) or complete remission with incomplete hematologic recovery (CRi), defined in accordance with the International Working Group (IWG) Response Criteria in AML.

All efficacy data collected, whether based on scheduled or unscheduled visits, will be included in the assessment of OCRR, with the exception of data collected following the start of subsequent AML therapy, which will not be included in the assessment of OCRR.

In all study parts, the primary analysis of OCRR will be assessed based on the evaluable for response (EFR) set with a sensitivity analysis based on the full analysis set (FAS).

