4.3 Patient Withdrawal and Replacement

Patients may withdraw from any part of the study at any time without penalty and for any reason without prejudice to his or her future medical care. The Investigator will advise the Sponsor of the withdrawal of any patient.

Patients must be withdrawn from study drug under the following circumstances:

- Patient voluntarily withdraws from study participation;
- Disease recurrence;
- Ineffective treatment;
- Unacceptable toxicity;
- Patient's withdrawal of consent;
- Death;
- Pregnancy (refer to section 6.3.1.11)
- Significant protocol deviation;
- Lost to follow-up;
- If deemed by the Investigator that it is not in the patient's interest to continue with the study.

Withdraws from study participation (follow-up permitted):

Patients withdrawing from the study drug will be encouraged where possible to return to the site for a study follow-up visit, in particular for safety evaluations, study assessments and survival follow-up.

Disease recurrence:

Sites should continue to perform efficacy assessments for patients achieving CR or CRi until disease recurrence (or death in the absence of recurrence) in accordance with IWG criteria for AML. Patients will be withdrawn from the treatment if there is evidence of disease recurrence as defined by IWG Criteria¹⁶ (Cheson, 2003).

Ineffective treatment:

The study drug may be discontinued in the event of:

- Treatment failure (in patients who do not achieve a PR or above after 4 cycles of treatment)
- Relapse, as defined by the IWG Response criteria (for patients with a CR or CRi)
- No longer meeting the criteria for a PR (in patients who were previously determined to have a PR)

Once ineffective treatment has been established, as described above, no further efficacy assessments are required.

Unacceptable toxicity:

If the symptoms are not controlled with standard treatments and are considered to be clinically significant, study drug will be stopped and the patient will be withdrawn from the study drug. Patients removed from study drug for unacceptable toxicity will be followed until resolution or stabilization of the AE.

Patients with a response (CR or CRi) withdrawn from the treatment prior to disease relapse should continue to be followed until the relapse in accordance with the study plan.

Consent Withdrawal:

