5.9.1 Permitted Concomitant Therapy

Therapies required to treat AEs, relieve disease symptoms, concurrent diseases and supportive care agents, such as antipyretics, antibiotics, blood transfusion, colony-stimulating factor, etc. will be permitted during the study.

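### A transfused platelet count can complete a partial remission in a patient who already meets the marrow rule, because transfusion-independence is required for CR but not for PR, and this can only raise the clinical benefit rate

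*SAP*

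**What the plan says.** SAP 3.1.1 and Protocol 6.2 define response in the same terms.

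- **CRi** needs marrow blasts below 5%, no blasts in blood, no Auer rods and no extramedullary disease. It sets no neutrophil or platelet threshold.
- **CR** builds on CRi: "Patient satisfies all of the criteria above and in addition has" neutrophils of at least 1.0 and platelets of at least 100 x 10^9/L, and "Transfusion-independence". No look-back period for that last condition is given.
- **PR** begins "A PR is defined as recovery of neutrophils to" the same 1.0, with platelets to the same 100. It adds a marrow rule. From a baseline of 50% or more, "the percentage of blast must decrease to a value between 5% and 25" per cent. From a lower baseline, "they must decrease by at least half to a value of more than 5" per cent. The third route is blasts below 5% with Auer rods persisting. Transfusion is not mentioned.

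On inputs, SAP 3.1.1 says of OCRR, under which these response categories are set out: "It will be derived programmatically from the BM aspiration and peripheral blood results". Protocol 5.9.1 permits therapies for "concurrent diseases and supportive care agents, such as antipyretics, antibiotics, blood transfusion" and colony-stimulating factor. Neither document sets a support-free interval before a response assessment.

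CBR counts CR, CRi and PR (SAP 3.1.3), using scheduled and unscheduled visits. TTR runs to the first CR, CRi or PR (SAP 3.1.5). Best response is the best single visit response, and no confirmation of PR is required. PR counts as non-response for OCRR.

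**The concern.** The safeguard against supported counts sits in the category where it cannot change CBR, and is missing from the one where it can. A patient in marrow remission whose counts depend on transfusion drops from CR to CRi and still counts in both OCRR and CBR. A patient with a PR-level marrow has no such fallback: the counts decide whether the visit is a PR or nothing.

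A program written to the SAP text would accept a platelet value of 105 on the day after a platelet transfusion as recovery. One such visit is enough. CBR is a secondary endpoint in both parts, and misclassification of this kind can only add patients to it. The cohorts are small, so one patient moves the estimate visibly. Such a PR may also be short-lived: Protocol 4.3 lists "No longer meeting the criteria for a PR (in patients who were previously determined to have a PR") among the grounds on which study drug may be discontinued.

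**Working it through.** The plan gives no expected CBR, no power and no transfusion frequency, so there is no planned figure to reproduce. The check compares the definitions and then sizes the effect.

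**1. Where counts decide membership of CBR**

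| Category | Count thresholds | Transfusion condition | If counts are not met | Effect on CBR |
|---|---|---|---|---|
| CR | 1.0 and 100 | Yes, undefined | Becomes CRi | None |
| CRi | None | None | Not applicable | None |
| PR | 1.0 and 100 | None | Not a response | Leaves CBR |

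PR is the only category in which a count decides CBR membership.

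**2. An illustrative patient.** Baseline blasts are 40%, and blasts at Cycle 3 Day 1 are 18%. Half of 40% is 20%; 18% is below that and above 5%, so the marrow rule is met. Neutrophils are 1.2. Platelets are 105 on the day after a platelet transfusion. As written, the visit is a PR. With an unsupported platelet count below 100 it would not be.

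**3. Shift per affected patient.** The shift is 100/n, provided the patient has no other visit that qualifies as PR, CRi or CR. If such a visit comes later, only TTR changes.

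- Part 2, n = 20: 100/20 = 5.0 points
- One Part 1 cohort, n = 6: 100/6 = 16.7 points
- All of Part 1, n = 24 to 18: 100/24 = 4.2 to 100/18 = 5.6 points

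**4. Part 2 intervals.** These use the planned two-sided 80% Clopper-Pearson method: lower limit Beta(0.10; x, n-x+1), upper limit Beta(0.90; x+1, n-x), with n = 20. The values of x are illustrative.

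| x/20 | CBR | 80% CI |
|---|---|---|
| 2 | 10% | 2.7 to 24.5% |
| 3 | 15% | 5.6 to 30.4% |
| 4 | 20% | 9.0 to 36.1% |
| 5 | 25% | 12.7 to 41.5% |

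One supported PR moves 4/20 to 5/20, and the whole interval moves up with it.

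**5. Frequency, by assumption only.** Let q be the share of patients meeting the PR marrow rule and s the share of those who reach the counts only with support. Expected inflation is 100qs points, and the chance of at least one case in 20 is 1 - (1 - qs)^20.

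- q = 0.10, s = 0.10: 1 point; 1 - 0.99^20 = 18%
- q = 0.20, s = 0.25: 5 points; 1 - 0.95^20 = 64%
- q = 0.30, s = 0.50: 15 points; 1 - 0.85^20 = 96%

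Neither q nor s is in the documents. The width of this range shows that the size of the effect cannot be predicted from them.

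**The case against.** Several points on the other side stand.

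- A reader might infer that supportive care can create a PR by itself. It cannot. All three PR routes need a marrow blast reduction, and support can supply only the count half.
- A reader might treat growth factor as part of the same inconsistency. It is not. CR has no condition on colony-stimulating factor either, so nothing was lost between CR and PR. A growth-factor rule would be an addition to the criteria, which is why it belongs in a sensitivity analysis only.
- A reader might infer that a raised CBR would steer the dose choice. The documents do not say so. The Part 1 primary endpoints are OCRR and safety, and the steering committee's notion of clinical benefit is left to a charter that is not available here.
- The 5 and 16.7 points are simply 1/n and would apply to any reclassified patient. CBR is descriptive, and no formal testing is planned.
- Supported PRs could be traced by hand. Concomitant therapies, derived response and the investigator's response are all listed (SAP 9.2).
- Both documents cite the IWG criteria, which may take recovery to mean unsupported recovery. That source cannot be checked here.

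These points limit the concern but do not remove it. The SAP says response is derived as it goes on to describe, and that description has no transfusion condition for PR. Listings let a reader spot a supported PR but do not correct the CBR table. It is also true that CR's own condition implies an input beyond marrow and blood results. That supports naming the input, since the SAP does not.

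**Conclusion.** The gap is real and narrow. As written, for a patient who already meets the PR marrow rule, a transfused platelet count can complete a PR, raise CBR and set an earlier TTR. The direction is always upward for CBR. The size is 5 points per affected patient in Part 2 and 16.7 points in a cohort of 6. How many patients would be affected is unknown, and any total rests on assumed values of q and s.

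OCRR does not change, because PR is a non-response and CR and CRi both count. A reader might conclude that the primary result is at risk, or that the Protocol's definition of PR should itself be made stricter. Neither follows. Protocol 3.4 makes failure to reach PR within 4 cycles a treatment failure that ends treatment, so a stricter definition in Protocol 6.2 would change a stopping rule. That is a clinical matter outside this point.

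**What to change.** Change the analysis classification in the SAP only.

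1. When deriving PR for CBR and TTR, do not count a platelet value as recovery if a platelet transfusion was given within a look-back window fixed before database lock. Seven days is an assumption; 7 to 14 is a plausible range. The rule concerns platelet transfusions, so red-cell transfusions do not trigger it.
2. Classify a PR-level marrow visit with no transfusion-free platelet count as not PR.
3. Report CBR with and without PRs whose counts were supported. Handle neutrophil values on colony-stimulating factor in that sensitivity analysis only.
4. Name the concomitant-medication and therapy eCRF pages as inputs to the programmed response. Protocol 5.9 already collects their start and stop dates, and CR's own transfusion criterion needs them too.

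Leave the treatment-failure and discontinuation rules unchanged. The sponsor should reconcile the PR wording in Protocol 4.3 and 6.2 with the SAP classification, so that the two uses of the term are distinguishable.

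The cost is a few SAP sentences, slightly more programming (a merge with data already collected), and a CBR that may be slightly lower. No new procedure is needed.

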4.1 Inclusion Criteria

Patients will be enrolled into the study only if they meet all of the following criteria:

1. Patients who are of or older than the legal age in the respective countries at the time when written informed consent is obtained
2. Patients who are able to understand and willing to sign the informed consent form (ICF)
3. Patients who are diagnosed with AML according to the 2016 revision to the World Health Organization classification of myeloid neoplasms and acute leukemia (refer to Appendix 1: WHO Classification of Acute Myeloid Leukemia)
4. Patients who have a sufficient archival or fresh BM aspiration sample for the evaluation of relevant exploratory endpoint.

Note: Patients who do not have sufficient archival BM aspiration sample and refuse to repeat the procedure may be enrolled in the trial only after written confirmation by ASLAN

5. Patients who are ineligible for standard treatment of AML including but not limited to the following conditions:
 - Newly diagnosed patients who are ineligible for standard therapy namely standard dose induction chemotherapy and reduced dose chemotherapy;
 - Patients who relapsed from prior remission;
 - Patients who failed to respond to prior therapy including chemotherapy, hypomethylating agents, and bone marrow transplantation.
6. Patients who have an Eastern Cooperative Oncology Group (ECOG) performance status of ≤ 2
7. Patients with adequate renal and hepatic function, as defined below:
 - Estimated Glomerular Filtration Rate (eGFR) or creatinine clearance (CrCl) (CrCL calculated by the Cockcroft and Gault method) ≥ 40 ml/min/1.73 m²
 - Total bilirubin, AST, and ALT $\leq 1.5 \times$ ULN

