6.2 Efficacy Variables

Efficacy will be evaluated with BM aspiration and peripheral blood results based on the IWG Criteria¹⁶ for AML (Cheson, 2003). For patients without sufficient archival BM sample, BM aspiration will be performed during Screening. All patients will receive bone marrow aspiration for efficacy assessment on Day 1 of Cycle 2, 3, 4, 5 and will be repeated every 12 weeks after Cycle 5. Patients who've already achieved CR could omit the bone marrow aspiration at subsequent visits if there is a normal complete blood count with differential of the peripheral blood. Investigator may perform more frequent exam if required based on clinical judgment. In order to address the primary objectives of the study, if treatment is interrupted for any reason, it is important that all planned safety and efficacy assessments are performed at the scheduled time, regardless of whether the patient is receiving study treatment, or not, at the time

BM aspiration smears will be processed locally.

Following treatment discontinuation, patients who have achieved a CR or CRi, will continue to be followed up for every 12 weeks to assess the relapse free survival. For patients who have not achieved a CR or CRi during treatment, no further follow-up is required following treatment discontinuation.

These criteria categorize the visit response into the following response classifications:

- CR with incomplete recovery of neutrophils and platelets (CRi):

Achievement of CRi requires patients to satisfy all of the following:

- A disappearance of blasts in the peripheral blood.
 - A decrease in BM blasts to <5% total BM nucleated cells demonstrated in BM aspirate.
 - Absence of Auer rods
 - No persistent extramedullary leukaemia
-
- Complete Remission:
Patient satisfies all of the criteria above and in addition has:
 - Recovery of Neutrophils to $\geq 1.0 \times 10^9/L$ and Platelets to $\geq 100 \times 10^9/L$
 - Transfusion-independence

 - Partial Remission:
A PR is defined as recovery of neutrophils to $\geq 1.0 \times 10^9/L$ and Platelets to $\geq 100 \times 10^9/L$ and either:

- If the pre-treatment bone marrow blast percentage was 50% to 100%, the percentage of blast must decrease to a value between 5% and 25%
 - If the pre-treatment BM blast percentage was 20% to less than 49%, they must decrease by at least half to a value of more than 5%
 - A reduction in BM blast cells to <5% but with persistence of Auer rods.
- **Treatment failure:**

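### The partial-remission bands leave two gaps (baseline 49 to <50%, and a fall to exactly 5% from a baseline of 20 to <49%), and a patient whose best visit falls in one is lost from the clinical benefit rate.

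*SAP*

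**What the plan says.** SAP 3.1 opens with a general reference: "Efficacy will be evaluated in accordance with the IWG Criteria". SAP 3.1.1 then writes the response classes out. Of the overall complete remission rate (OCRR) it says "It will be derived programmatically from the BM aspiration and peripheral blood results", and the visit classes follow in the same section.

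- **CR and CRi** share a marrow condition: "A decrease in BM blasts to <5% total BM nucleated cells demonstrated in BM aspirate".
- **PR** always needs count recovery ("A PR is defined as recovery of neutrophils to" at least 1.0 x 10^9/L and platelets to at least 100 x 10^9/L), plus one of three marrow conditions:
  - upper band: "If the pre-treatment bone marrow blast percentage was 50% to 100%, the percentage of blast must decrease to a value between 5% and 25" (percent);
  - lower band: "pre-treatment BM blast percentage was 20% to less than 49%, they must decrease by at least half to a value of more than 5" (percent);
  - marrow blasts below 5% with Auer rods still present.
- **Treatment failure** is the best response of a patient who has met none of CR, CRi or PR after four cycles.

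Protocol 6.2 carries the same lower band ("pre-treatment BM blast percentage was 20% to less than 49" percent), so it does not repair the SAP. Best response is the best visit (SAP 3.1.1). CBR counts only CR, CRi and PR (SAP 3.1.3). Time to response (TTR) runs to the first of these (SAP 3.1.5).

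**The concern.** A response scale should give every marrow value a class and should not rank a better value below a worse one. These bands fail on both counts.

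First, the lower band stops below 49% and the upper band starts at 50%, so a baseline from 49% up to 50% has no blast-reduction route to PR. Second, from a baseline of 20 to <49%, PR needs more than 5% and CR/CRi needs less than 5%. A marrow value of exactly 5% therefore earns nothing, while 6% earns PR. The Auer-rod route does not help, because it also needs less than 5%. The bands also disagree with each other: if the upper band's range includes its ends, exactly 5% is PR from a baseline of 50% but not from 48%.

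What is at stake is CBR, a secondary endpoint in both parts, together with the best-response table and the TTR listing. Readings of 49% and 5% are plausible when blasts are recorded as whole percentages, and 5% is the remission boundary itself.

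**Working it through.** The plan gives no figure to reproduce: the study is not formally powered and no CBR is assumed. The check applies the written rule and counts what it leaves out.

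**Inputs.** PR, CR and CRi rules from SAP 3.1.1. Part 2 size 20 and Part 1 cohort size 6 from SAP 6.1. Two-sided 80% Clopper-Pearson interval from SAP 7.3. Assumptions: recovered counts, no Auer rods, no peripheral blasts, no extramedullary disease, and the upper band's 5% and 25% included.

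**Step 1: single cases.**

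| Baseline % | Follow-up % | Class as written |
|---|---|---|
| 48 | 24 | PR |
| 49 | 24 | none |
| 50 | 25 | PR |
| 30 | 6 | PR |
| 30 | 5 | none |
| 30 | 4 | CR if transfusion-independent, otherwise CRi |
| 50 | 5 | PR |

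**Step 2: whole-percent grid.**
- Upper band as written: 51 baselines (50 to 100) x 21 follow-up values (5 to 25) = 1071 PR cells.
- Lower band as written: for each baseline b from 20 to 48, follow-up runs from 6 to floor(b/2), giving floor(b/2) - 5 cells. The sum is 486 - 145 = 341.
- Total as written: 1071 + 341 = 1412.
- Gap cells: 29 (baseline 20 to 48, follow-up exactly 5) + 20 (baseline 49, follow-up 5 to 24) = 49.
- Total with the gaps closed: 1412 + 49 = 1461. Share changed: 49/1461 = 3.4%.
- At 0.1% recording: 2270 of 138351 cells, or 1.6%.
- If the upper band's ends are excluded: 49 + 51 (exactly 5%) + 51 (exactly 25%) = 151 whole-percent cells change.

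No cell moves into or out of CR/CRi. Cells are not probabilities, so these counts show the extent of the gaps and not how often patients will fall in them.

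**Step 3: effect on CBR.** One patient is 1/20 = 5.0 points in Part 2 and 1/6 = 16.7 points in a Part 1 cohort. The 80% limits are the 10% quantile of Beta(x, n - x + 1) and the 90% quantile of Beta(x + 1, n - x). Starting from an assumed 4 of 20 as written:

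| Gap patients (assumed) | CBR with gaps closed | 80% CI |
|---|---|---|
| 0 | 4/20 = 20.0% | 9.0 to 36.1% |
| 1 | 5/20 = 25.0% | 12.7 to 41.5% |
| 2 | 6/20 = 30.0% | 16.6 to 46.7% |

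**Step 4: effect on TTR.** Take a baseline of 40%, 5% at Cycle 2 Day 1 (study day 29), and 4% with CR/CRi at Cycle 3 Day 1 (day 57). Response is listed at day 57. Had the first value been 6%, it would be listed at day 29. The difference is 57 - 29 = 28 days.

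**The case against.** The gaps themselves are not in dispute. The case against concerns weight and remedy.

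- **The programming sentence has OCRR as its subject, and PR does not enter OCRR.** That is so. But SAP 3.1.1 sets out every visit class beneath that sentence, and SAP 9.2 lists an IWG response separately from the investigator's assessment of it. A literal derivation of PR is the natural reading, though an inferred one.
- **Response is tied to the IWG criteria, which may close the bands.** That source is not available here, so nothing is claimed about it. If the sponsor relies on it, the SAP should state the bounds, because the written text gives different ones.
- **Few patients can be affected.** This stands. Count recovery is required, and best response is the best visit, so a count-recovered patient going 40% to 15% to 5% is already PR at 15%. The counts of gap patients above are illustrations.
- **The patient remains visible.** Marrow results and the investigator's response are listed (SAP 9.2), and waterfall plots are drawn (SAP 7.4). This limits the harm but does not correct the CBR table.
- **Other cases are also unclassified.** Marrow below 5% without Auer rods, but with persisting peripheral blasts or extramedullary disease, meets no response class. A baseline below 20% has no blast-reduction route to PR, although Protocol 4.1 states no blast minimum and admits, for example, "Patients who relapsed from prior remission". The documents do not show whether that limit is intended, so it is raised only as a query.

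**Conclusion.** The concern holds. Both gaps are in the written rule, in the SAP and the protocol alike, and following the rule puts a marrow value of 5% in a worse class than 6%. Each patient whose best visit lies in a gap lowers CBR by 5.0 points in Part 2 or 16.7 points in a six-patient cohort. These figures assume that no patient is excluded from the evaluable set; with exclusions each patient counts for slightly more.

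The severity is minor. The number affected may be zero. OCRR does not change. CBR is descriptive, with no test or threshold (SAP 6.5). TTR is only listed (SAP 7.5). Dose intensity does not change, because PR and treatment failure share the same four-cycle window (SAP 3.2.2).

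**What to change.** In SAP 3.1.1, before database lock and for the analysis of CBR, best response and TTR only:

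1. Extend the lower baseline band to run from 20% up to, but not including, 50%.
2. Treat exactly 5% alike in both bands, so that 5% or more counts as PR when the other conditions are met. State at the same time that the upper band includes its ends.
3. Report in the clinical study report how many patients change class.
4. Ask the sponsor to state the intended classification for baselines below 20%. No new PR route is proposed.

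The protocol uses the same PR term for treatment failure and discontinuation (synopsis under Study Duration, 3.4 and 4.3, with the definition in 6.2). Those passages must be reconciled with the analysis definition; no clinical rule is proposed here.

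The cost is a short change to the SAP wording and a small change to the response program, with no new data. Until the protocol is reconciled, the SAP will differ from Protocol 6.2, with which it now agrees, and a patient could be PR for CBR yet a treatment failure under the protocol. That difference must be documented.
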